6.2 Study Design

This Phase I single site open-label clinical trial will evaluate the use of Tice® BCG in healthy adult participants as a challenge model for future assessment of TB drugs. Subjects (N=10) will be divided into two groups, where group 1 will receive INH in the dose of 300 mg for three days post BCG injection and group 2 (control arm) will not receive any treatment. All groups will receive a dose titration of 2×10^6 cfu of Tice® BCG intradermally as noted in the following table:

	Group 1	Group 2
N	5	5
Tice® BCG Dose	2×10^6 cfu	2×10^6 cfu
INH Dose	300 mg/3 days	Control

Participants will have follow-up clinic visits that will include: clinical assessments, AE/SAE review, ID challenge assessments, blood draws for immunogenicity and mycobacteria assays, skin biopsies, general exams and PPD skin testing.

7.0 STUDY POPULATION

Ten healthy, HIV and TB uninfected, male and non-pregnant female subjects, 18 to 45 years old, inclusive, will be enrolled from a single study site in Seattle, Washington. The target population should reflect the Seattle King County community. Recruitment materials may be dispersed in the community and participants from other research registries may be contacted. Enrollment will occur over a 2-month period. Consent will be required for enrollment.

8.0 SUBJECT ELIGIBILITY

Inclusion and Exclusion Criteria must be assessed by a medically licensed study clinician to make medical diagnoses.

8.1 Inclusion Criteria

Participants must meet all of the following criteria to participate in this study.

1. Provide written informed consent prior to initiation of any study procedures,
2. Are males or non-pregnant females between the ages of 18 and 45 years, inclusive,
3. Women of childbearing potential* in sexual relationships with men must use an acceptable method of preventing conception** from 30 days prior to 3 months after Tice® BCG administration,

**Not sterilized via tubal ligation, bilateral oophorectomy, hysterectomy or successful Essure® placement (permanent, non-surgical, non-hormonal sterilization) with documented radiological confirmation test at least 90 days after the procedure, and still menstruating or < 1 year of the last menses if menopausal).*

***Includes, but is not limited to, sexual abstinence, monogamous relationship with vasectomized partner who has been vasectomized for 6 months or more prior to the subject receiving Tice® BCG, barrier methods such as condoms or diaphragms with spermicide or foam, effective intrauterine devices, NuvaRing®, and licensed hormonal methods such as implants, injectables or oral contraceptives ("the pill").*

4. For women of childbearing potential, negative serum pregnancy test at screening and negative urine pregnancy test within 24 hours prior to enrollment and Tice® BCG administration,
5. Are in good health, as judged by the investigator and determined by vital signs (oral temperature, pulse, and blood pressure), medical history and physical examination,
6. Have a negative HIV-1 ELISA test,
7. Have negative serology tests for hepatitis B surface antigen and hepatitis C virus antibody,
8. Have a negative QuantiFERON®-TB Gold test,
9. Negative is defined as Nil response < 0.8 IU/ml and TB Antigen response minus Nil response <0.35 IU/mL or TB Antigen response minus Nil response > 0.35 IU/mL and < 25% of Nil response and Mitogen response minus Nil response > 0.5 IU/ml,
10. Have a urine dipstick for protein less than 1,
11. Have a urine dipstick negative for glucose,
12. Ability to understand and complete all study visits as required per protocol and be reachable by telephone.

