10.2 Screening

Those who consent will be considered for eligibility and will undergo evaluations and assessments (screening process). Screening procedures include review of the participant's medical history and concomitant medications, and collecting their vital signs (oral temperature, pulse, blood pressure) and height and weight (to calculate BMI). The Participant will undergo a physical examination within 42 days prior to receiving Tice® BCG. Female participants of childbearing potential must have a negative serum pregnancy test at screening and a negative urine pregnancy test within 24 hours prior to enrollment and receipt of Tice® BCG. Participants must have a urine dipstick for protein < 1 and negative for glucose at

screening. Participants will have their blood drawn via venipuncture to be screened for HIV, hepatitis B surface antigen, antibody to hepatitis C virus, and QuantiFERON®-TB Gold Test. Results of these screening tests must be negative.

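### Criterion 9's definition of a negative QuantiFERON result contradicts itself: one branch needs Nil above 1.4 IU/mL, the only Nil limit is 0.8, and the scope of the Mitogen condition is left open

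*Combined protocol and SAP*

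**What the plan says.** Criterion 8 in section 8.1 requires volunteers to "Have a negative QuantiFERON®-TB Gold test". Criterion 9 then defines the term in a single sentence. It opens with "Negative is defined as Nil response < 0.8 IU/ml and TB Antigen response minus Nil response <0.35 IU/mL" and continues after an *or* with "TB Antigen response minus Nil response > 0.35 IU/mL and < 25% of Nil response and Mitogen response minus Nil response > 0.5 IU/ml", so that the Mitogen condition comes last, joined by a further *and*. There are no brackets, and nothing says which conditions apply to both branches.

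The list is conjunctive: "Participants must meet all of the following criteria to participate in this study". Section 10.2 repeats the requirement for the screening blood tests, which include QuantiFERON: "Results of these screening tests must be negative". Section 11.2 says the same. No other section defines a negative result, and no section gives a rule for an invalid or indeterminate one.

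**The concern.** The two figures attached to Nil do not fit together. The alternative branch is written for people with a high Nil, while the opening clause limits Nil to a low value. The closing Mitogen clause can be read as applying to the whole definition or only to the branch it follows, and the reading changes who is eligible.

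QuantiFERON is the only laboratory test for TB infection scheduled at screening. No screening skin test is planned, and exclusion 35 in section 8.2 rules out a PPD in the two months before BCG. For a volunteer with no relevant history, TB-uninfected status before a live BCG injection therefore rests largely on this sentence. Section 10.8 uses the assay again after a positive PPD and gives no separate definition, so the same wording would presumably be used there.

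**Working it through.** The plan gives no derived figure to reproduce here. The check is of the logic, with one line of arithmetic.

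**Inputs, all from criterion 9 (IU/mL).** Let D stand for TB Antigen minus Nil.
- n: Nil < 0.8
- A: D < 0.35
- B: D > 0.35 and D < 0.25 × Nil
- C: Mitogen minus Nil > 0.5

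**Step 1: when B can be met.** B needs room between 0.35 and 0.25 × Nil. So 0.25 × Nil > 0.35, which gives Nil > 0.35 / 0.25 = 1.4. At the stated limit, 0.25 × 0.8 = 0.20, which is below the 0.35 floor. B and n can never both hold. Any Nil limit at or below 1.4 has the same result.

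**Step 2: bracketings.** Three test results are used:
- X: Nil 0.1, D 0.05, Mitogen minus Nil 0.1
- Y: Nil 2.0, D 0.4, Mitogen minus Nil 5
- Z: Nil 2.0, D 0.1, Mitogen minus Nil 5

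For Y and Z, 25% of Nil is 0.5. Y meets B (0.35 < 0.4 < 0.5). Z meets A but not n.

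| Bracketing | Second branch | X | Y | Z |
|---|---|---|---|---|
| n and (A or B) and C | empty | not negative | not negative | not negative |
| (n and A) or (B and C), the ordinary *and*-before-*or* order | needs Nil > 1.4 | **negative** | negative | not negative |
| n and (A or (B and C)) | empty | **negative** | not negative | not negative |
| ((n and A) or B) and C | needs Nil > 1.4 | not negative | negative | not negative |

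**Step 3: what each one means.**
- Row 1: the alternative branch does nothing. The rule reduces to n and A and C, and the only possible error is to exclude someone the branch was meant to admit.
- Row 2: the main branch has no Mitogen check, so X passes. At Nil 2.0 the larger TB response (Y) is negative and the smaller one (Z) is not.
- Row 3: the alternative branch is empty and the main branch has no Mitogen check.
- Row 4: the branch can be met and Mitogen covers both branches, but the inversion between Y and Z remains.

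Reading strictly left to right classifies X, Y and Z as in row 4. It also rejects a result with Nil 0.1, D 0.05 and Mitogen minus Nil 5, because 0.05 is not below 0.25 × 0.1 = 0.025.

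**Step 4: the boundary.** A uses a strict < 0.35 and B a strict > 0.35. A value of exactly 0.35 is in neither branch under any bracketing.

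**The case against.** The strongest defence is that a sensible reader takes the sentence as three checks in turn: Nil, TB minus Nil, and Mitogen. On that reading (row 1) the rule works, nobody is wrongly admitted, and the fault is a surplus clause. Section 8.0 has a medically licensed clinician assess eligibility, and Appendix A sends the assay to a local laboratory that may report its own interpretation. This stands in part. If row 1 was meant, the harm is limited to over-exclusion. But the text does not establish row 1, which makes a whole written branch meaningless, and the protocol does not defer to the laboratory's interpretation.

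A reader might infer that the rule must either contain a dead branch or drop the Mitogen check. That is too strong. Row 4 does neither, although it has its own inversion and nothing in the punctuation points to it.

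A reader might also infer that the protocol lets people with failed tests into a live challenge, or that one such person, being 1/5 = 20% of an arm, would distort the CFU comparison. The documents do not support this. They give a Mitogen threshold but never call it a validity control, so treating a low value as a failed test is an interpretation. They give no frequency for low values, and a low value is not itself evidence of TB infection. History of TB (exclusion 1), immunosuppression (exclusion 20) and a prior positive PPD or BCG (exclusion 33) are screened separately. The 20% figure would describe any eligibility error with five per arm.

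The gap at 0.35 is trivial: such a result is simply not negative, so the volunteer is not eligible.

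**Conclusion.** The point holds as an internal inconsistency in an operative eligibility rule. The contradiction between Nil > 1.4 and Nil < 0.8 follows from the protocol's own figures and needs no outside source. The consequence depends on the bracketing: over-exclusion only (row 1), a negative call with Mitogen minus Nil at or below 0.5 (rows 2 and 3), or an inverted rule at high Nil (rows 2 and 4). None gives every clause a workable meaning, and no other section repairs the sentence.

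No size is put on the effect on safety or on the CFU endpoint, because the documents do not say how often volunteers have a high Nil or a low Mitogen value. Nor do they show which threshold was intended. The conclusion assumes only that criterion 9 supplies the meaning of negative for criterion 8, which its wording and position indicate.

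**What to change.** Rewrite criterion 9 with explicit brackets:
- Apply the Mitogen minus Nil condition to both branches.
- Reconcile the 0.8 Nil limit with the 25%-of-Nil branch against the assay's own interpretation table: either correct the limit or delete the branch. A limit at or below 1.4 leaves the branch empty.
- As a minor tidy-up, assign exactly 0.35 to one branch.

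The cost is one eligibility sentence, processed as a protocol amendment. Sample size, visits and assays do not change.

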8.2 Exclusion Criteria

Participant cannot meet any of the following criteria and must be excluded from participating in this study.

1. Have a history of suspected, confirmed, treated or have other evidence of active tuberculosis, Symptoms may include recurrent fever, fatigue, night sweats, weight loss, oral ulcers, diarrhea, nausea, vomiting, or bleeding,
2. Have any systemic symptoms* within 72 hours before Tice BCG administration or signs of lymphadenopathy, hepatosplenomegaly, or pulmonary disease by physical examination on day of Tice BCG administration,
**Includes fever, chills, malaise, fatigue, headache, night sweats, weight loss, nausea, vomiting, bleeding, diarrhea, abdominal pain, rhinorrhea, cough, wheezing, or shortness of breath.*
3. Have history of any significant acute or chronic medical conditions* or need for chronic medications that, in the opinion of the investigator, will interfere with immunity or affect safety,
**Includes, but is not limited to, disorders of the liver, kidney, lung, heart, or nervous system, or other metabolic or autoimmune/inflammatory conditions. Have any history of excessive scarring or keloid formation.*
4. Have household contact or occupation involving significant contact with someone who is immunocompromised,
**Includes persons with HIV, AIDS, or active cancer; infants (children < 1 year); pregnant women; or persons who are immunosuppressed for approximately 6 weeks (during the time of active ID lesion drainage).*
5. Have a history of epilepsy (does not include febrile seizures as a child),
6. Have a pacemaker, prosthetic valve, or implantable cardiac devices,
7. Have a history of bleeding disorder,
8. Have a known allergy to any Tice BCG components (glycerin, asparagine, citric acid, potassium phosphate, magnesium sulfate, iron ammonium citrate, and lactose),
9. Received blood products or immunoglobulin within 6 months prior to Tice BCG administration,
10. Received immunotherapy within one year prior to Tice BCG administration,
11. Received or plan to receive live attenuated vaccines 4 weeks before or after Tice BCG administration,
12. Received or plan to receive inactivated or killed vaccines 2 weeks before or after Tice BCG administration,

13. Plans to enroll in another clinical trial* that could interfere with safety assessment of the investigational product at any time during the study period,
**Includes trials that have a study intervention such as a drug, biologic, or device.*

14. Received an experimental agent* within 30 days prior to Tice BCG administration or planned receipt of an experimental agent within 90 days after Tice BCG administration,
**Includes vaccine, drug, biologic, device, blood product, or medication.*

15. Have a history of use of a systemic antibiotic within 14 days prior to Tice BCG administration or planned use of a systemic antibiotic for 3 months after Tice BCG administration,

16. Have any medical, psychiatric, occupational, or behavioral problems that make it unlikely for the subject to comply with the protocol as determined by the investigator,

17. Are health care providers at the highest risk of acquiring MTB infection, such as pulmonologists performing bronchoscopies on TB patients,

18. Are breastfeeding or plan to breastfeed at any given time throughout the study,

19. Have long term use* of high dose oral or parenteral glucocorticoids**, or high-dose inhaled steroids***.
**Defined as taken for 2 weeks or more in total at any time during the past 2 months.*
***High dose defined as prednisone ≥ 20 mg total daily dose, or equivalent dose of other glucocorticoids.*
****High dose defined as > 800 mcg/day of beclomethasone dipropionate or equivalent. If short term corticosteroids are given, then the subject should not receive Tice® BCG or have blood collected for immunogenicity studies within 1 week of steroid administration.*

20. Have immunosuppression or are taking systemic immunosuppressants as a result of an underlying illness or treatment,

21. Use of anticancer chemotherapy or radiation therapy (cytotoxic) within 36 months prior to Tice® BCG administration,

22. Any active neoplastic disease,

23. Have a pulse rate less than 50 bpm or greater than 100 bpm,

24. Have a systolic blood pressure less than 90 mm Hg or greater than 140 mm Hg,

25. Have a diastolic blood pressure less than 50 mm Hg or greater than 90 mmHg,

26. Have a WBC less than $4.0 \times 10^3/\mu\text{L}$ or greater than $10.5 \times 10^3/\mu\text{L}$,

27. Have hemoglobin less than $11.5 \times 10^3/\mu\text{L}$ (female) or less than $12.5 \times 10^3/\mu\text{L}$ (male),

28. Have a platelet count less than $140 \times 10^3/\mu\text{L}$,

29. Have a creatinine greater than 1.30 mg/dL,

30. Have an ALT (SGPT) greater than 40 IU/L (female) or greater than 55 IU/L (male),

31. Have known HIV, Hepatitis B, or Hepatitis C infection,

32. Have a history of alcohol or drug abuse in the last 5 years,

33. Have had a positive PPD skin test in the past or received BCG vaccine (BCG vaccination history will be determined by self-report, country of birth, and/or evidence of BCG scar),

34. Have a BMI > 35 ,

35. PPD skin test within 2 months prior to Tice BCG administration or planned receipt during the study other than from participation in this study,

36. Oral temperature $\geq 100.4^\circ\text{F}$ ($\geq 38.0^\circ\text{C}$) or other symptoms of an acute illness within 3 days before Tice BCG administration. (Subject may be rescheduled),

37. Any medical disease or condition that, in the opinion of the investigator, is a contraindication to study participation*,
**Includes medical disease or condition that would place the subject at an unacceptable risk of injury, render them unable to meet the requirements of the protocol, or may interfere with the evaluation of responses or their successful completion of the study.*

38. Have any condition that would, in the opinion of the site investigator, place the subject at an unacceptable risk of injury or render the subject unable to meet the requirements of the protocol or compromise the interpretation of data or the scientific integrity of the protocol.

9.0 RECRUITMENT

Participants will be recruited from the Seattle King County area. Recruitment materials may be posted in community areas such as, but not limited to: the campuses of Fred Hutchinson and University of Washington, and community businesses that allow the posting of flyers. Enrollment may also come from participants of other research studies and registries.

All recruitment methods and will be reviewed and approved by the IRB prior to approaching participants. The participants from other studies or repositories must have granted consent to allow being contacted and given information about other research studies. The method of contact is determined by the IRB's approval per the other research studies protocols and registries as they may have certain limitations.

The gender and ethnic and racial demographics will reflect the Seattle King County community at large.

10.0 STUDY PROCEDURES AND EVALUATIONS

10.1 Consent

Informed consent is a process that is initiated prior to the individual's agreeing to participate in the study and continuing throughout their study participation. The consent process will include the explanation of the research study to the participant and answer any questions that may arise. The study team member who conducts the consent process will be medically qualified to answer any health concerns, risks and possible benefits of participation in this study. The consent form will be provided to the subject which they may share with their families. The consent form describes in detail the study procedures and risks. The participant will be given an adequate amount of time to review the consent form prior to giving consent by signing the form. Consent forms are IRB reviewed and approved prior to being distributed to participants. They are written documentation of informed consent and the participant is required to sign it prior to enrolling in the study. The subjects may withdraw consent at any time throughout the course of the study. A copy of the informed consent document will be given to the participants for their records.

10.2 Screening

Those who consent will be considered for eligibility and will undergo evaluations and assessments (screening process). Screening procedures include review of the participant's medical history and concomitant medications, and collecting their vital signs (oral temperature, pulse, blood pressure) and height and weight (to calculate BMI). The Participant will undergo a physical examination within 42 days prior to receiving Tice® BCG. Female participants of childbearing potential must have a negative serum pregnancy test at screening and a negative urine pregnancy test within 24 hours prior to enrollment and receipt of Tice® BCG. Participants must have a urine dipstick for protein < 1 and negative for glucose at

screening. Participants will have their blood drawn via venipuncture to be screened for HIV, hepatitis B surface antigen, antibody to hepatitis C virus, and QuantiFERON®-TB Gold Test. Results of these screening tests must be negative.

10.3 Group Assignment

After the participant meets enrollment criteria, they are randomly assigned by a computer program to 1 of the 2 groups. In both groups, participants will be immunized intradermally with a single dose of 2×10^6 cfu Tice® BCG.

- Group 1 subjects will receive INH dosages on Days 4, 5, and 6.
- Group 2 (control arm) will not receive INH.

10.4 Study Drug Administration

Tice® BCG and INH preparations will be performed by the participating clinical study site pharmacist and administration will be performed by a study clinician licensed to administer study product.

10.4.1 *BCG injection (all participants)*

One intradermal injection of Administration of BCG 2×10^6 cfu Tice® BCG in the deltoid region, Following administration of Tice® BCG, intradermal (ID) site reactions will be assessed for at least 30 minutes.

10.4.2 *INH (Group 1 only)*

For the 5 participants assigned to Group 1, they will take INH: oral tablets of either three 100mg tablets (300mg) or one 300mg tablet on days 4, 5, and 6 post BCG dosing.

10.5 Study Duration

The participants will come to the study clinic 17 times to undergo study procedures. Additional visits may be required if they experience an abnormal ID challenge site. The maximum study duration will be 22 weeks (about 6 months). A screening visit, BCG dosing visit and 15 follow up visits within 4 months will occur after skin biopsy.

10.6 Evaluations

10.6.1 *Physical Examination and Clinical Assessments*

A physical examination will be performed within 42 days prior to getting BCG and at the final study visit. Participants medical history, concomitant medications, their vital signs (oral temperature, pulse, blood pressure), and height and weight (to calculate Body Mass Index (BMI)) will be collected. Participants will be assessed for lymphadenopathy if indicated based on review of interim medical history and clinical assessment. A medically licensed research team member will review the participants health status and eligibility at the clinic visits.

10.6.2 *Participant Self-monitoring AEs/SAEs and Health Status Records*

Participants will be asked to record their solicited local and systemic reactions, any unsolicited AEs/SAEs (pain, tenderness and drainage) and concomitant medications throughout the study.

They can optionally record their oral temperature as well. They will be sent a redcap survey to record this information. They will be instructed on how to measure and record AEs/SAEs.

